### ***LP Procedure***

Procedure will follow the standard protocol used at CAMC CCC for pediatric patients for outpatient LP. Immediately prior to the start of the procedure, a final verification process is to be conducted to confirm correct patient and procedure. The patient will be sedated via anesthesia team. Moderate conscious sedation to limit movement during the LP will be performed with propofol with or without sevoflurane gas with all processes and monitoring adhering to CAMC CCC's standard of care.

Patient will then be positioned for lateral decubitus positioning. Appropriate hand hygiene is to be completed prior to procedure. The operator is to wear a mask and sterile gloves for this sterile procedure. If randomized to lidocaine-obtaining group, Sham-EMLA cream will be removed and an approximately 1 ml of lidocaine 1% is to be injected into the subcutaneous tissue. If randomized to EMLA group, the cream will be removed with no further local site analgesic being introduced.

The lumbosacral area is to be surgically prepped with Betadine or 2% chlorhexidine and draped in the usual fashion. An appropriate needle will be introduced into L3-L4 or L4-L5 interspace and CSF fluid is to be obtained. If applicable, the appropriate dose of chemotherapy per patient's protocol is to be administered into the intrathecal space. The needle is to be withdrawn using standard technique. Sedation will then be stopped by anesthesia team.

### ***Post-LP***

The patient will be directed to lay still for 30 minutes post-procedure before sitting or standing. Standardized instructions for at home PRN pain control will be provided to the patient, typically acetaminophen (15mg/kg) every 6 hours as needed for pain relief. The post-LP, at home pain medications will not be provided by the study.

#### ***30-60 min Pain Level Assessment:***

Pain level will be measured at 30-60 minutes after waking up from procedure sedation, prior to departure from the CCC, using Wong-Baker Faces Pain Rating Scale. A numeric value is to be collected. The child will self-select (either verbally or by pointing to) the face that best describes the pain he/she is feeling.

#### ***24 hour Pain Level Assessment:***

Pain level will be measured at 24 hours. A paper form of the Wong-Baker Faces Pain Rating Scale will be sent home with the patient and parent/guardian will be directed to complete it 24

hours following the procedure. The parent/guardian will be directed to have their child to self-select (either verbally or by pointing to) the face that best describes the pain the child is feeling. The patient or parent/guardian will receive a log to document pain score at 24 hours and PRN pain medications; this will be used to record information that will be shared with study personnel during the follow-up phone call.

*24 hour PRN Pain Control Assessment:*

A paper log will be sent home with the parent/guardian. On this log, they will be directed to record all PRN pain control medications, doses, times, the patient used within the 24 hours following the LP. A clinician/study team member will call the patient's parent/guardian within 72 hours to obtain the patient's 24-hour pain rating and PRN pain medicine information.

***Subsequent LP***

Patients will be in the study until they have completed 2 LPs, unless if a patient chooses to withdraw. If a patient decides to withdrawal from the study, we will document the date of and reason for the withdrawal.

For the second LP post-enrollment, patients and parent/guardian will be informed of study continuation and be given the opportunity to ask questions to study investigators about the study. The second LP will default to the local analgesic that was not received during the first LP. All procedures described above will be followed for this second LP.

**Data Collection/Instrumentation**

Data will be collected from CAMC Cerner Millennium EMR and CAMC/CAMC Children's Cancer Center records. Collected data variables will include:

- Date of Visit/LP
- Demographic data
  - Name
  - Age
  - Sex
  - Race/ethnicity
  - Weight (kg)
- Valid Telephone number
- Diagnosis
- LP sequential number since study enrollment: first or second
- Randomized to initially received: EMLA or Lidocaine
- For the current LP: received EMLA or Lidocaine
- Time of EMLA / EMLA sham administration
  - Calculated time from EMLA administration to LP
- Amount of Lidocaine
- Number of needle pricks of lidocaine
- Signs of pain with lidocaine

- Provider that performed LP
- Time of LP
- Number of attempts with LP needle
- Any complications during LP (describe)
- Pain score prior to procedure (baseline)
- Pain score at 30-60 minutes waking up from post LP sedation
- Pain score at 24 hours post LP
- PRN medication requirement within 24 hours post-procedure
- Adverse reaction to local analgesic

## **Data Analysis**

CAMC CHERI Outcome Research will perform statistical analysis for the study. Descriptive statistics will be computed. Continuous variables will be presented as means and standard deviations and if non-parametric, as medians and interquartile ranges. Categorical variables will be reported as frequencies and percentages. Each patient will serve as his or her own control; we will compare pain scores and prn medication usage for lidocaine to a patient's pain scores and prn medication usage when receiving EMLA. Tests for carryover and period effects will be conducted prior to treatment effects analyses.

Pain scores between the LPs (lidocaine vs EMLA local analgesia) will be compared using nonparametric test for matched or paired data, Wilcoxon signed-rank test. Nonparametric tests will be for statistical analyses of pain scores, as the Wong-Baker Faces Pain Rating Scale consists of ordinal values. We will analyze pain scores obtained at baseline, 30 – 60 minutes post waking after LP sedation, and 24 hours post-LP separately. Young children ( $\geq 6$  years) and children/adolescents (6-18 years) pain scale data will be analyzed jointly. In addition, if an age subgroup ( $< 6$  years or 6-18 years) has an  $n > 5$  then the age subgroup's pain scale measures will be analyzed separately.

We will analyze prn pain medication usage by comparing the amount of acetaminophen (mg/kg) reported as being taken between the two LPs local analgesics (lidocaine vs EMLA). We will compare the prn pain medication amount for each local analgesic via a paired t-test (or Wilcoxon signed-rank test if prn medication data is non-parametric). Other analgesics (if any) will be analyzed separately, in a similar manner.

A p-value of  $< 0.05$  will be used to determine statistical significance. The statistical program IBM-SPSS (Version 19) will be used for all analyses.

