### **Sample**

Twenty patients will be invited to participate. A total of 17 patients are required to have a 90% percent chance of detecting a 2-point difference (standard deviation = 2.25) on the Wong-Baker Faces Pain Rating Scale (i.e. the difference from a 4 “hurts little more” to a 2 “hurts little bit”), when using paired 2-tail analysis (Wilcoxon signed-rank test). Sample size calculated

using G\*Power 3.1. We will enroll up to 20 patients to allow for patient withdrawals/loss to follow-up prior to the second LP. The accrual goal of 20 patients is comparable to other studies examining LP analgesics as well as a feasible goal with CAMC CCC's current patient load. A maximum of 50 patient records will be screened will to determine study eligibility.

*Setting:*

Charleston Area Medical Center, Women and Children's Cancer Center (CCC).

We are also inviting Pediatric Oncology at Marshall University/Cabell Huntington Hospital also to participate in the study. They will obtain approval from their local IRB. They will send de-identified study patient information to our institutions for analysis. All appropriate approvals (and data use agreements) will be obtained prior to their participation.

*Inclusion Criteria:*

- Pediatric cancer patients (aged 3-18) with a diagnosis of leukemia or lymphoma
- Patients are expected to receive serial (i.e. > 1) LP as outpatients in CCC in the course of 12 months for diagnostic and/or treatment purposes

*Exclusion Criteria:*

- Patients not in the age range
- Non-cancer patients
- Allergy to amide anesthetics
- Patients treated with class I and III anti-arrhythmic drugs (eg, amiodarone, bretylium, sotalol, dofetilide)
- Patients with congenital or idiopathic methemoglobinemia

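### Period and carryover tests are planned with no stated consequence, and the treatment tests for pain and PRN use ignore period and sequence

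*Combined protocol and SAP*

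**What the plan says.** Each child has two LPs, one under each analgesic, in randomised order. The Data Analysis section opens its inferential plan with "Tests for carryover and period effects will be conducted prior to treatment effects analyses". It gives no method for these tests, no threshold of their own, and no action to take on a positive or negative result.

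The treatment comparisons follow. Pain scores at each time point "will be compared using nonparametric test for matched or paired data, Wilcoxon signed-rank test". PRN acetaminophen in mg/kg is compared "via a paired t-test (or Wilcoxon signed-rank test if prn medication data is non-parametric"). For age subgroups with more than five children, "the age subgroup's pain scale measures will be analyzed separately".

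The Data Collection/Instrumentation list already contains both variables that a crossover analysis needs: "LP sequential number since study enrollment: first or second" and "Randomized to initially received: EMLA or Lidocaine".

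The Sample section sizes the trial for the unadjusted test: "A total of 17 patients are required to have a 90% percent chance of detecting a 2-point difference" with an SD of 2.25, "when using paired 2-tail analysis (Wilcoxon signed-rank test"). Up to 20 children are enrolled to allow for losses before the second LP. The randomisation text balances the two arms by blocks.

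**The concern.** Two gaps sit together.

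- **The preliminary tests lead nowhere.** If the period or carryover test is positive, the analyst could ignore it, adjust for period, or drop the second-LP data. That choice would be made with the data in view.
- **The treatment tests leave out information already collected.** If pain shifts by *s* points from LP1 to LP2 whatever the analgesic, the EMLA-minus-lidocaine difference moves by −*s* in the EMLA-first children and +*s* in the lidocaine-first children. The pooled differences spread out, so the signed-rank and paired t-tests lose power and their intervals widen. If the sequences have unequal numbers of completers, the shifts do not cancel and the estimate is biased. Blocked randomisation secures balance at entry, not among children who complete both LPs.

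The Background reports that an EMLA benefit was not sustained over repeat LPs. That is a treatment effect that changes between LPs, not a common shift. Period adjustment does not remove it, and it is not used here as evidence for one.

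**Working it through.** **Inputs.** From the Sample section: effect 2 points, SD 2.25 (read as the SD of paired differences), two-sided test, 17 required, up to 20 enrolled. From Data Analysis: significance at 0.05. Assumed, because the documents give none: a common LP1-to-LP2 shift *s* of 0, 0.5, 1, 1.5 or 2 points.

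**The plan's own figure.** Standardised effect 2/2.25 = 0.889. Using noncentral-t power with effective sample size N × 3/π (signed-rank efficiency under normality), power is 0.898 at N = 16 and 0.917 at N = 17. The stated 17 reproduces.

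**Simulation.** At least 40,000 trials per scenario. EMLA-minus-lidocaine differences are normal with SD 2.25, mean 2 − *s* in one sequence and 2 + *s* in the other. Exact critical values: signed-rank 34 (n = 17) and 52 (n = 20); rank-sum U ≤ 15 (9/8), ≤ 23 (10/10), ≤ 14 (10/7). The rank-sum test compares LP1-minus-LP2 differences between sequences, so a common shift cancels. Ranges cover both shift directions.

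| Completers | Test | s = 0 | s = 1 | s = 1.5 | s = 2 |
|---|---|---|---|---|---|
| 9/8 | signed-rank | 91% | 85–89% | 77–85% | 64–78% |
| 9/8 | rank-sum | 90–91% | 90–91% | 90–91% | 90–91% |
| 10/10 | signed-rank | 96% | 93% | 89% | 82% |
| 10/10 | rank-sum | 95% | 95% | 95% | 95% |
| 10/7, unfavourable direction | signed-rank | 91% | 80% | 67% | 49% |
| 10/7, favourable direction | signed-rank | 91% | 92% | 91% | 88% |
| 10/7 | rank-sum | 89% | 89% | 89% | 89% |

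At *s* = 0.5 the signed-rank test has 89–91% (9/8) and 95% (10/10).

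**Bias at 10/7.** (10 − 7)/17 × *s* = 0.18 points per 1-point shift.

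**How likely is 10/7?** If 20 enter 10/10 and 3 are lost at random, all three come from one sequence with probability 2 × C(10,3)/C(20,3) = 240/1140 = 0.21; otherwise the split is 9/8. Averaged over splits and directions, signed-rank power is 91%, 87%, 80% and 70% at *s* = 0, 1, 1.5 and 2, against 90% for rank-sum.

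**95% CI half-width at 9/8 (t-based).** Unadjusted: t(16) × √(V/17), with V = 2.25² + (2*s*)² × 72/(17 × 16). This gives 1.16, 1.27, 1.40 and 1.57 points at *s* = 0, 1, 1.5 and 2. Adjusted: 0.5 × t(15) × 2.25 × √(1/9 + 1/8) = 1.17 at every *s*.

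**Null size of signed-rank at 9/8.** About 4.3%, 2.9%, 1.8% and 0.9% at *s* = 0, 1, 1.5 and 2; the exact value at *s* = 0 is 4.5%. The test becomes conservative.

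**A test-then-adjust rule** (rank-sum if the period test has p < 0.05, otherwise signed-rank) has power of 89–91% at 9/8 and 86–92% at 10/7, with null size at most 5%.

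**Carryover test as a gate.** With the SD of differences held at 2.25, patient totals have SD 2.25 × √((1 + r)/(1 − r)) for within-child correlation r. Over assumed r from 0 to 0.7, power to detect a 2-point carryover is 11–40% with 17 children and 12–47% with 20.

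**Face scale.** Assumptions: per-visit SD 2.25, correlation 0.5, means 2 and 4, scores rounded to 0, 2, …, 10. With no shift, signed-rank has 87%, 92% and 87% at 9/8, 10/10 and 10/7; rank-sum has 87%, 92% and 85%. At 9/8 with a 2-point shift: signed-rank 59–76%, rank-sum 81–87%.

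**The case against.** The loss depends on a shift that no document supplies. LP1 and LP2 are counted from enrolment, and children may already have had LPs, so a large common shift is not obvious. At 0.5 points the loss is negligible. At 1 point with 20 balanced completers the planned test still has 93%, and averaged over splits at 17 it loses only about 3 percentage points to rank-sum (87% against 90%). The 49% figure needs 17 completers, all three losses from one sequence, the unfavourable direction and a 2-point shift. In the favourable direction at 10/7 the planned test does slightly better than the proposed one at 1 and 1.5 points. Validity is not threatened at these splits. One could also read the preliminary tests as implying adjustment when positive, which performs nearly as well; then one sentence is all that is missing.

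Most of this stands and limits the weight of the point. It does not remove it. The plan does not state an adjustment rule, so the favourable reading has to be supplied by the reader. By planning a period test the sponsor accepts that a shift is possible. The remedy costs at most 2 points of power in these scenarios if there is no shift, and protects against a much larger loss if there is one.

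**Conclusion.** The point holds and should be fixed, as an inexpensive improvement and not as a flaw that invalidates the trial. No consequence is attached to the period or carryover tests, and the treatment tests use neither period nor sequence although both are recorded.

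The size depends on the assumed shift. With 17 completers near balance, a 1-point shift takes power to 85–89% and a 2-point shift to 64–78%, against 90–91% for the adjusted test. With 20 completers split 10/10, the planned test is clearly below 90% only near 2 points. A significant result from the planned test near balance is not undermined. These figures assume normal, continuous differences; on the face scale power is generally lower, with the same pattern. No power claim is made for PRN use, because the Sample section states power for pain only.

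**What to change.** 1. **Pain at 30–60 minutes and 24 hours.** Make the treatment test a Wilcoxon rank-sum comparison of within-child LP1-minus-LP2 differences between the EMLA-first and lidocaine-first sequences. Report the Hodges-Lehmann treatment difference (half the between-sequence shift) with a 95% CI. The baseline comparison can stay as planned.
2. **PRN acetaminophen.** Use a two-sample t-test of LP1-minus-LP2 mg/kg between sequences, or rank-sum if skewed.
3. **Preliminary tests.** Replace the sentence with: *Period and carryover estimates with 95% CIs will be reported descriptively and will not determine which analysis or which data are used.* Add that a treatment effect that changes between LPs cannot be separated from carryover in this two-period design.
4. **Sensitivity.** Keep the signed-rank and paired t-tests as sensitivity analyses.
5. **Small age subgroups.** Use signed-rank or description. With 6 or 7 children the smallest exact two-sided rank-sum p is 2/20 = 0.10 (3/3) or 2/35 = 0.057 (4/3), against 2/64 = 0.031 and 2/128 = 0.016 for signed-rank.
6. **Sample section.** Restate power for the new test: about 90% at 9/8, 95% at 10/10 and 89% at 10/7 on continuous scores; 87%, 92% and 85% on the face scale with no shift, with the assumptions named.

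A prespecified rule that adjusts when the period test is positive is an acceptable alternative. It is about as powerful near balance and somewhat weaker at 10/7 in the unfavourable direction.

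**Cost.** Revised wording in two sections and no new data. If there is no shift, power falls from 91.1% to 90.6% at 9/8, 95.8% to 94.8% at 10/10, and 91.1% to 89.0% at 10/7. The overall analysis and the small subgroups would use different tests.

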## **2. HUMAN SUBJECTS**

### **A. Subject Population**

- i. Study patients will be comprised of children (3-18 years old) with leukemia or lymphoma receiving lumbar punctures as part of their management. It will be clearly described verbally and in writing (in the consent and assent) that choosing not to

participate will not affect their care at CAMC CCC. Research activity and data collection will only begin after informed consent and if applicable, the assent is signed. Prospective participants will not be vulnerable to coercion or undue influence.

**B. Recruitment Method**

- i. Cancer patients who receive care at CAMC CCC will be approached regarding possible study participation at a prescheduled CCC visit. A member of the study team will describe the study to the patient and parent/guardian, answer all questions, and obtain the necessary informed consent, if the patient and parent/guardian wish to participate in the research. Written consent will be obtained (from patient if  $\geq 18$  years, or from parent/guardian if the patient  $< 18$  years). Written assent will be obtained from patients aged 7-17 years old, verbal assent will be obtained from patients aged 3 to 6 years old. Written consent/assent will be obtained prior to randomization.

**C. Benefits**

- i. Our study might help identify which analgesic method, whether EMLA cream or lidocaine injection, prior to lumbar puncture provides the most post-procedural pain relief. This will help future patients of the CAMC CCC by providing the most appropriate pain relief when undergoing lumbar punctures.

**D. Risks and Discomforts**

- i. Lumbar punctures are routine procedures for childhood cancer patients. Since both EMLA and lidocaine injection are routinely used for this procedure, there is no added risk to their standard care regimen.

**E. Privacy**

- i. The patients (and parents/guardians) will be consented and assented in an examination room or other private room during their visit at CAMC CCC with the door closed. The study aims, protocol, and goals will be described to them by study personnel.

**F. Confidentiality**

- i. Privacy interests of the participants in the study will be protected at all times. All identifying patient information will remain in the PI's locked office and on a password protected computer in a password-protected file, if electronic. Identifying patient information will only be accessed by study investigators. Paper forms will be shredded, and electronic files will be deleted at the time publication. All results will be reported with no identifiers. Any study information sent from outlying study sites will be de-identified and sent securely (for example password protected file in encrypted email).

**G. Costs to Subjects**

- i. The patient/patient's guardian will be responsible for all co-pays and deductibles associated with routine care billable to the insurer. There will be no additional financial burden to the patient for participating in this study. Sham-EMLA cream and Tegaderm will be funded through departmental funds and/or grant support and will not be billed to patients or their insurance.

## Appendix A

©1983 Wong-Baker FACES Foundation. [www.WongBakerFACES.org](http://www.WongBakerFACES.org)  
Used with permission.

### Instructions for Usage

Explain to the person that each face represents a person who has no pain (hurt), or some, or a lot of pain.

Face 0 doesn't hurt at all. Face 2 hurts just a little bit. Face 4 hurts a little bit more. Face 6 hurts even more. Face 8 hurt a whole lot. Face 10 hurts as much as you can imagine, although you don't have to be crying to have this worst pain.

Ask the person to choose the face that best depicts the pain they are experiencing.

Obtained from <http://www.WongBakerFACES.org>
